6 DESCRIPTION OF DEVICE

[figure not shown]
6.1 INTENDED USE

The TearCare™ System is indicated for the application of localized heat when the current medical community recommends the application of a warm compress to the eyelids of adult patients. Such applications would include Meibomian Gland Dysfunction (MGD), Dry Eye, or Blepharitis.

6.2 DEVICE DESCRIPTION

The TearCare™ System is comprised of the following components:

- iLid™ Device
- TearCare System, which includes the following:
 - Controller
 - Charging nest
 - Charging adapter
 - Clip

6.3 INSTRUCTIONS FOR USE

Instructions for Use are provided with each TearCare System.

6.4 SUMMARY OF THE TRAINING AND EXPERIENCE NEEDED FOR USE OF DEVICE UNDER INVESTIGATION

This is a single-center study, conducted by [name]. [name] is a co-inventor of the TearCare System and is familiar with its proper use. He will review the Instructions for Use in advance of initiating the investigation.

6.5 DESCRIPTION OF ASSOCIATED MEDICAL OR SURGICAL PROCEDURES

Within 10 minutes following the 15-minute TearCare session, the investigator will perform manual Meibomian gland expression of all 4 eyelids under topical anesthesia with ophthalmic tetracaine 0.5% drops.

7 PRIOR INVESTIGATIONS

7.1 PRECLINICAL TESTING

The TearCare System has been tested extensively on the bench to demonstrate that it meets all specified safety and performance requirements. The following testing and analyses was performed:

- Thermal Requirements: Testing was performed to demonstrate that the TearCare System meets the minimum, maximum and nominal therapeutic temperature requirements.
- Software Functionality: Testing was performed to demonstrate that the software in the TearCare Controller and iLid Devices meet all software requirements.
- Electrical Safety: Testing was performed to demonstrate that the System meets the electrical safety requirements specified in IEC 60601-1.
- Electromagnetic Compatibility: Testing was performed to demonstrate that the System meets the electromagnetic requirements specified in IEC 60601-1-2.
- Biocompatibility: All patient-contacting materials were reviewed to confirm that that they are biocompatible for short-term (<24 hours), skin contact.

- Mechanical Strength: Testing was performed to demonstrate that the system meets mechanical strength requirements.
- Shipping, Storage, and Shelf-Life Testing: Testing was performed to demonstrate that the TearCare System meets shipping, storage and shelf-life requirements.

The TearCare System passed all pre-clinical testing, demonstrating that the system meets its requirements.

7.2 PREVIOUS CLINICAL EXPERIENCE

The TearCare System has been studied in a single center pilot study conducted in 2017. The results were published in *Clinical Ophthalmology*²⁷ and are summarized below.

Objectives

The objective of this study was to evaluate the clinical utility, safety, and effectiveness of the TearCare™ System compared to standardized warm compress therapy.

Subjects

Twenty-four (24) subjects with symptoms of dry eye in the past 3 months were enrolled. The average age was 67.6 ± 13.5 years (range 29.7 – 89.8 years). All subjects were female, white and not Hispanic or Latino. All subjects had a SPEED score ≥ 6 at the Baseline visit. All subjects had a Tear Break-up Time (TBUT) of <10 seconds in at least one eye at baseline and 72% (17/24) had a Schirmer 1 score (non-anesthetized) of ≤ 10 mm in at least one eye at the Baseline visit.

Methods

This was a prospective, single-center, randomized, parallel-group, clinical trial. Subjects with DED were randomized to either a single TearCare treatment conducted at the clinic or 4 weeks of daily warm compress therapy. The TearCare procedure consisted of 12 minutes of thermal eyelid treatment immediately followed by manual expression of the meibomian glands. Warm compress therapy consisted of once daily application of the compresses to the eyelids for 5 minutes. Subjects were followed to 6 months post-treatment. The primary effectiveness endpoint was defined as change from baseline to 4 weeks for Tear Break-up Time (TBUT). Secondary effectiveness endpoints included meibomian gland assessment, corneal and conjunctival staining scores, and assessment of dry eye symptoms using validated questionnaires. Safety was evaluated by collecting device-related adverse events, intraocular pressure, and best spectacle-corrected Snellen Visual acuity.

Results

Twenty-four subjects were enrolled and completed 6 months follow-up. Data are summarized in Table 1 below.

At 1 month follow-up, TearCare subjects demonstrated an improvement from baseline in mean (\pm SD) TBUT of 11.7 ± 2.6 seconds compared with an average worsening of -0.3 ± 1.1 seconds for subjects in the warm compress group ($p<0.0001$). Significantly greater improvements in the change from baseline in meibomian gland scores, as well as corneal and conjunctival staining scores were observed in the TearCare group. Subjects in the TearCare group also showed significantly greater improvement in dry eye symptoms as measured by the three questionnaires.

No adverse events were reported in either group.

A large rectangular area of the page is completely blacked out, indicating that the original content has been redacted for confidentiality.

Conclusions

The TearCare Group consistently showed a significant improvement between the baseline and 4 weeks follow-up for all outcome measures, whereas the Warm Compress group did not. For all outcome measures, the TearCare Group's mean change between baseline and 4 weeks follow-up was better than the Warm Compress group. These results were maintained out to 6 months.

This pilot study provided preliminary evidence of the safety and effectiveness of the TearCare device in relieving the signs and symptoms of dry eye.

8 STUDY ENDPOINTS

8.1 EFFECTIVENESS ENDPOINTS

[figure not shown]
The primary effectiveness endpoint of the study is the change from baseline to 4 weeks in Tear Break-Up Time (TBUT).

Secondary effectiveness endpoints include the change from baseline to follow-up in the following:

- **Meibomian Gland Assessment**²⁸ scores for the following:
 - The number of Meibomian glands yielding clear liquid secretions (grade 3)
 - The number of glands secreting any liquid (clear or cloudy with grade 2 or 3)
 - The total Meibomian Gland Score
- **Dry Eye Symptoms and Quality of Life**, as measured by:
 - The Standard Patient Evaluation of Dry Eye (SPEED) II questionnaire²⁹, which measures the severity and frequency of dry eye symptoms
 - Ocular Surface Disease Index (OSDI) Questionnaire³⁰. The OSDI consists of 12 questions to assess ocular symptoms (the Ocular Symptoms subscale), their impact on patient vision-related functioning (Vision Related Function subscale), and environmental factors triggering the symptoms (Environmental Triggers subscale).
 - Symptom Assessment in Dry Eye (SANDE) Questionnaire.^{31, 32} The SANDE is a 2-question survey which uses a visual analog scale to assess the frequency and severity of dry eye symptoms
- Corneal & conjunctival staining scores

8.2 SAFETY ENDPOINTS

Safety of the TearCare System will be evaluated by evaluating changes in the following measures:

A series of 10 horizontal black bars of varying lengths, each preceded by a small black square, representing a list of safety endpoints that have been redacted for confidentiality.

- Device-related adverse events
- Best spectacle-corrected Snellen visual acuity

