One of the most commonly prescribed treatments for evaporative dry eye and meibomian gland dysfunction is the use of warm compresses. It is believed that the heat from warm compresses helps melt the oily obstructions in the meibomian glands and helps reduce gland inflammation, thereby helping to restore the ability of the meibomian glands to effectively secrete oil onto the tear film and prevent rapid tear evaporation. It has been shown that warm compress therapy can lead to improved lipid production and flow on to the tear film.^{8,9,10} This improved lipid delivery is associated not only with an improvement in the profile of the tear film but also an improvement in patient symptoms.^{11,12,13} The tear film is demonstrably thicker and more stable with an increased contribution of lipid to its surface.^{14,15,16} However, many

[figure not shown]

factors contribute to poor penetration of warm compress therapy in the dry eye population. More specifically, warm compress therapy has failed to achieve widespread acceptance among patients because:

- It is inconvenient and disruptive to a patient's schedule
- The temperature necessary to achieve an effective AND safe compress is difficult to achieve and maintain at home^{17,18,19}
- Warm compresses, when used at home, tend to cool quickly thereby diminishing their efficacy
- Some patients may over heat the compress putting them at risk for injury^{20,21}
- Patients are not able to enhance the effect by expressing molten secretions from their meibomian glands as a physician routinely does for his/her patients.

Various approaches to heating the eyelids have been proposed, but often they may be too cumbersome or costly for patients.^{22,23,24,25,26}

Sight Sciences has developed a novel device, the TearCare™ System, to deliver controlled, precise heat to the meibomian glands for 12 minutes in the monitored setting of an ophthalmologist or optometrist office. (Refer to Section 6, Description of Device, below.) The TearCare session is then followed by routine manual expression of the meibomian glands by the physician. The goal of this is to more effectively and conveniently treat dry eye with an accepted proven treatment.

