9 STUDY DESIGN

This is a prospective, non-randomized, single-center case series study. No specific attempts will be made for minimization of bias, such as blinding or masking.

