11.6 FOLLOW-UP VISITS

Prior to the Visit: Reminder Call

Since dry eye drops and lubricants can affect the endpoint assessments, it is important to call subjects a few days before their follow-up visits to remind them that on the day of the Follow-up visit, they should not to use any of these products before the Follow-up visit.

Order of Procedures During the Follow-Up Visit

Follow-up exams should not be performed by the clinician who performed the TearCare procedure.

A large block of text is completely redacted with black bars, representing a list of procedures or steps.

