11.8 WITHDRAWAL AND DISCONTINUATION

All subjects have the right to withdraw at any point during the treatment without prejudice. The investigator can discontinue any subject at any time if continued participation in the study would result in harm to the subject. All efforts should be made by the investigator to retain the subject in the study. If a subject withdraws prematurely from the study, a genuine effort must be made to determine the reason(s) the subject discontinued the study. The reason must be recorded in the subject's file and on the End of Study Form.

If a subject withdraws from the study prior to receiving the TearCare, then that subject may be replaced in the study by a newly enrolled subject.

12 ADVERSE EVENTS (AEs)

Adverse Events are defined below. Adverse events that occur in the eye during the trial, whether they are considered to be device related or not, must be documented in the subject's records. Date of the event, its severity, treatment (if any) and the assessed relationship of the event to the study device will be recorded on the Adverse Event Form. Conditions which exist at the time the subject is enrolled do not need to be recorded on the Adverse Event Form as adverse events unless they increase in severity during the study.

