12.3 REPORTING ADVERSE EVENTS AND UNANTICIPATED ADVERSE DEVICE EFFECTS

Identification, collection and reporting of adverse event information is the responsibility of the principal investigator. The investigator records the date of the event, its severity, treatment (if any) and the assessed relationship of the event to the study device on the Adverse Event Case Report Form (AE CRF).

All unanticipated adverse device effects (UADE) will be reported as soon as possible, but no later than 10 working days after the investigator first learns of the event, to the following two entities:

1. The study sponsor - E-mail the AE CRF to [contact]; and
2. The reviewing IRB – per the IRB's instructions.

The sponsor will conduct an evaluation of unanticipated adverse device effects. If the sponsor determines that an unanticipated adverse device effect presents an unreasonable risk to subjects, parts of the investigation presenting risks will be terminated. Termination will occur not later than 5 working days after the sponsor makes such a determination and not later than 15 working days after the sponsor first received notice of the effect.

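### The only visible adverse-event safety endpoint counts device-related events, although ocular events of any cause are already recorded, so the safety figure rests on an attribution this unmasked single-arm design cannot check

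*Combined protocol and SAP*

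**What the plan says.** **Endpoint.** Section 8.2 lists "Device-related adverse events" and best spectacle-corrected visual acuity, after a block of redacted entries. The synopsis gives the same two items, and no redaction is marked in that row.

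**Collection.** The opening of section 12 is wider: "Adverse events that occur in the eye during the trial, whether they are considered to be device related or not, must be documented". Severity, treatment and assessed relationship go on the form for each event. The adverse-event definition in section 12.1 needs no causal link. The same section defines an adverse device effect by a possible relation to the device.

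**Who records.** Section 12.3 states: "Identification, collection and reporting of adverse event information is the responsibility of the principal investigator". It adds that the investigator records "the assessed relationship of the event to the study device on the Adverse Event Case Report Form (AE CRF").

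**Design.** Section 9 describes a single-center, non-randomized case series and says: "No specific attempts will be made for minimization of bias, such as blinding or masking". Section 6.4 says that the named investigator "is a co-inventor of the TearCare System and is familiar with its proper use". Section 11.6 gives one partial safeguard: "Follow-up exams should not be performed by the clinician who performed the TearCare procedure".

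**Analysis.** Section 14.4 plans basic descriptive statistics only. Sections 14.1 and 14.3 set no hypothesis and no pass/fail rule.

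**The concern.** Safety of re-treatment is part of the stated objective (section 4). An endpoint limited to device-related events passes every event through a causality judgement before it is counted. A randomized trial can limit the damage from a poor judgement, because all-cause rates can be compared between arms. Here there is no second arm, no masking, and no visible provision for independent review of ordinary events. The person responsible for adverse-event information is the investigator, and the named investigator has an interest in the device.

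The threshold is also left open. Section 8.2 does not say whether an event counts when a relation is merely possible, as in the section 12.1 definition of an adverse device effect, or only when it is probable or definite. The same set of events could yield different endpoint counts under these readings.

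What is at stake is the reported figure. It could be zero while ocular events stand in the subjects' records. No decision rule depends on it.

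**Working it through.** **1. Endpoint against data collected**

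| | Synopsis and 8.2 | Section 12 |
|---|---|---|
| Events covered | Device-related | Ocular, related or not |
| Relatedness | Decides whether an event counts | Recorded as an attribute of the event |
| Threshold | Not stated | 12.1 defines an adverse device effect by possible relation |

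The visible endpoint is a subset of what is already collected. The gap lies in the endpoint definition and the reporting, not in data capture.

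**2. Inputs for size**

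- Sample size: 12, the size of the pilot's TearCare arm (section 14.2). Section 11.2 says up to 12, so fewer is possible. The values 10 and 8 below are my assumptions. The plan derives no sample size by formula, so there is no calculation to reproduce.
- Event experience: the pilot followed 24 subjects for 6 months and reported no adverse events in either group (section 7.2).
- The single event below is an illustration, not a forecast.

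**3. Formulas (Clopper-Pearson, two-sided 95%)**

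- 0 of n: upper limit = 1 − 0.025^(1/n). For n = 12: 1 − 0.025^(1/12) = 0.265.
- 1 of n, lower limit: 1 − 0.975^(1/n). For n = 12: 0.002.
- 1 of n, upper limit: the p that solves (1 − p)^n + n·p·(1 − p)^(n−1) = 0.025. For n = 12: p = 0.385.

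**4. Results when one subject has an event and only the attribution differs**

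| Enrolled | Counted as related | Not counted |
|---|---|---|
| 12 | 1/12 = 8.3% (0.2% to 38.5%) | 0/12, upper limit 26.5% |
| 10 (assumed) | 1/10 = 10.0% (0.3% to 44.5%) | 0/10, upper limit 30.8% |
| 8 (assumed) | 1/8 = 12.5% (0.3% to 52.7%) | 0/8, upper limit 36.9% |

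At 12 subjects, each subject reclassified moves the rate by 1/12 = 8.3 percentage points.

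**5. What the pilot's zero shows**

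Twelve of the 24 pilot subjects were in the TearCare arm. By the formula above, zero events in 12 is compatible with a true rate of up to 26.5%. The pilot makes an event look unlikely but does not rule one out.

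**The case against.** The strongest reply is that the data are collected anyway and that nothing in the documents says other events will go unreported. The pilot also used device-related adverse events as a safety measure, yet its summary reports no adverse events, without a relatedness qualifier. This is fair. A reader might infer that non-device events will be suppressed, or that the co-inventor will misattribute them. The documents support neither inference. What stands is that no visible text commits to summarising all documented ocular events.

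Other replies:

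- **Redaction.** A wider endpoint may be hidden in section 8.2. That cannot be excluded, although the synopsis row shows the same two items with no redaction marked.
- **Safeguards.** A different clinician performs follow-up exams, any sight-threatening event is reportable as an unanticipated adverse device effect, and the sponsor evaluates such effects. These help, but the first does not say who judges relatedness, and the others do not reach an ordinary abrasion or eyelid inflammation.
- **Gland expression.** A reader might infer that harm from manual expression escapes the endpoint, because section 5 says: "The TearCare session is then followed by routine manual expression of the meibomian glands by the physician". The text does not establish this. Section 7.2 counts expression as part of the pilot's TearCare procedure, and the sections and form that could settle it (11.5.3, 12.2, the adverse event form) were not supplied.
- **Eyelid events.** Reading section 12 as excluding the lids is strained, since the eye exam in Appendix A (24.1) covers the lid margins.
- **Legitimacy.** A device-related endpoint is an acceptable choice in a small descriptive series. It is less informative as the only adverse-event endpoint.

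**Conclusion.** The point holds as a minor one. On the visible text, the adverse-event endpoint is narrower than the events recorded, depends on an attribution that a single unmasked arm cannot check, and has no stated threshold. For 12 subjects and one event, the consequence is the difference between 8.3% and zero, with wide intervals in both cases.

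The conclusion rests on two assumptions: that the redacted entries in section 8.2 contain no all-cause adverse-event endpoint, and that the missing sections do not define device-related. The size also depends on an event occurring, which the pilot's record makes less likely. Nothing here shows that events would be lost, hidden or wrongly attributed. Visual acuity does not depend on attribution, but it may miss a transient event.

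**What to change.** In the synopsis and section 8.2, define the adverse-event endpoint as all documented ocular adverse events, including eyelid and periocular ones, regardless of relationship. Report it as the number and percentage of subjects; an exact 95% interval is optional. As a subset, show the events judged at least possibly related to the device or the TearCare procedure, using the section 12.1 threshold.

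This removes the judgement from the headline count. The subset still depends on it, and the all-cause count has no comparator, so it describes what happened without showing what the device caused.

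The cost is wording in two places and, if the adverse event form records relationship to the device alone, one more entry on it. Sample size, visits and treatment do not change. The downside is a few more events to list and a possibly less favourable safety figure.

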9 STUDY DESIGN

This is a prospective, non-randomized, single-center case series study. No specific attempts will be made for minimization of bias, such as blinding or masking.

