10 STUDY SELECTION CRITERIA

10.1 INCLUSION CRITERIA

For inclusion in this study, subjects must meet all of the following criteria:

1. Previously enrolled in the TearCare arm of the TearCare Pilot Study (protocol number 05429)
2. Reports dry eye symptoms within 3 months of the baseline examination with a Standard Patient Evaluation for Dryness (SPEED) score ≥ 6
3. TBUT of <10 seconds in at least one eye
4. Willing to comply with the study, procedures, and follow-up
5. Willing and able to provide consent

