15 MONITORING PROCEDURES

15.1 MONITORING TO BE CONDUCTED DURING THE INVESTIGATION

- Since [name] has already conducted dry-eye related clinical trials with Sight Sciences, no site qualification visit will be required.

- Sight Sciences personnel will meet with the investigator(s) and clinical study staff at the time the site begins to enroll in order to ensure that subjects are being properly selected and that study data are being correctly recorded.
- Sight Sciences personnel or designee will visit the clinical site periodically during the study to review and/or collect the Case Report Forms.
- At the conclusion of the trial there will be a study closure visit during which, the following items will be reviewed and actions performed:
 - A final inspection of the study binder
 - Accountability and return of all devices and study materials to the sponsor
 - Close-out notification to the IRB

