15.2 EXTENT OF SOURCE DATA VERIFICATION

The study CRF will serve as both the source document and the CRF.

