24.3 TEAR BREAKUP TIME (TBUT)

TBUT is an indicator of tear film instability and detects dry eye syndrome due to evaporative causes such as meibomian gland disease.

To measure TBUT, instill fluorescein into the eye using 2% fluorescein solution prepared according to the method defined by Gyau et al.³⁸ Ask the subject to blink several times. Record the break-up time using a stopwatch. Repeat the test 3 times and take the average of the 3 measurements.

[figure not shown]

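### Section 9 disclaims all bias control while section 11.6 imposes one; reconcile them, and have follow-up examiners sign TBUT, gland and staining scores before earlier values are opened

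*Combined protocol and SAP*

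**What the plan says.** Section 9 describes a single-center, non-randomized case series and states: "No specific attempts will be made for minimization of bias, such as blinding or masking". Section 11.6 nevertheless requires: "Follow-up exams should not be performed by the clinician who performed the TearCare procedure". The order-of-procedures text that follows in 11.6 is redacted.

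The primary endpoint (section 8.1) is the within-subject change in TBUT from baseline to 4 weeks. Appendix A, section 24.3, has an observer time it: "Record the break-up time using a stopwatch" and "Repeat the test 3 times and take the average of the 3 measurements". Section 24.2 grades gland secretions from 0 to 3 by appearance. Section 24.4 grades corneal and conjunctival staining by eye. These two exams supply five secondary scores, three for the glands and two for staining.

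Entry requires "TBUT of <10 seconds in at least one eye" (section 10.1), and every subject receives the procedure (section 11.2). On records, section 15.2 says "The study CRF will serve as both the source document and the CRF", and section 15.1 says sponsor staff or a designee "will visit the clinical site periodically during the study to review and/or collect the Case Report Forms". Section 14 sets no hypothesis and no success criterion, and plans descriptive summaries only.

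**The concern.** Two things look wrong. First, a blanket statement that nothing will be done about bias cannot stand beside a rule whose evident purpose is to limit examiner bias. A reader of the final report would not know which describes the study.

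Second, the rule in 11.6 controls who examines and not what that person has seen. A stopwatch reading or an appearance grade can be pulled by knowledge of the subject's own previous value. The study has no concurrent comparison, so a systematic shift at follow-up passes whole into the mean change. That mean change is the main effectiveness result of a study whose stated objective (section 4) includes effectiveness. Section 6.4 also identifies the investigator as a co-inventor of the device, which makes simple, visible safeguards more valuable. Treatment cannot be hidden in a single-arm study, but a subject's earlier readings can be.

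**Working it through.** **The plan's own figure.** There is none to reproduce. The 12 subjects are the size of the earlier TearCare arm (section 14.2), with no power or precision calculation, and the plan gives no figure for measurement bias.

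**Step 1: the texts side by side.**
- Section 9: no attempt at bias control.
- Section 11.6: the treating clinician is kept away from follow-up exams.
- Neither section, in the visible text, says whether the follow-up examiner may see earlier values.

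The first two cannot both be right as written. The third is a gap in the visible text only, because part of 11.6 is redacted.

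**Step 2: how a shift reaches the endpoint.** Let b0 be the mean reading error at baseline and b1 the mean reading error at follow-up. Then

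observed mean change = true mean change + (b1 − b0).

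The shift does not shrink as subjects are added. Averaging three readings reduces random error but leaves a tendency common to all three. The sign is not fixed: expecting improvement would push b1 up, while anchoring on a low baseline value would pull it down. At 4 weeks the baseline value is the only earlier reading within this study. At 3 and 6 months the earlier follow-up values are added.

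**Step 3: scale against the pilot change.** Section 7.2 gives a mean TBUT improvement of 11.7 s at 1 month, SD 2.6 s. The drift is an assumption, shown as a range:
- 0.5 / 11.7 = 4%
- 1 / 11.7 = 9%
- 2 / 11.7 = 17%

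These percentages scale inversely with the change actually seen. If re-treatment gave half the pilot change (11.7 / 2 = 5.85 s, also an assumption), they would double, to about 9% at 0.5 s and 34% at 2 s.

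**Step 4: scale against sampling error, for illustration only.** With n = 12 and the pilot SD:
- SE = 2.6 / √12 = 0.75 s
- 95% half-width = 2.201 × 0.75 = 1.65 s, with t on 11 degrees of freedom
- Drift as a share of the half-width: 0.5 s is 30%, 1 s is 61%, 2 s is 121%
- Actual coverage of a nominal 95% interval, from the noncentral t with noncentrality drift/SE: about 91%, 77% and 32%

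The plan does not commit to reporting an interval, so Step 4 gives a sense of scale and does not describe a planned analysis.

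**The case against.** The strongest case on the other side has five parts.

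- **The plan already controls examiner bias.** A reader of section 9 alone might infer that the study has no protection at all. Section 11.6 does not support that: separating treatment from follow-up assessment is a real control. This stands, and it is why the conflict between the two sections comes first.
- **Access to earlier values is not shown.** A reader might infer from section 15.2 that examiners read earlier results because the case report form is also the source document. That section concerns source verification and says nothing about which pages are open at a visit. Section 15.1 allows forms to be collected during the study, the form layout is not given, and separate visit pages may already exist. This also stands. The point rests on the lack of a visible withholding rule, not on evidence that values are seen. Periodic review or collection is, however, not a rule that withholds them.
- **The redacted text might contain such a rule.** It might. Section 9 would then contradict that rule as well, and would still need correcting.
- **Withholding values leaves most cues in place.** Examiners can know that all subjects were treated and that TBUT was below 10 s in at least one eye at entry. This stands: the exact earlier value is only one part of what they know.
- **Nothing is decided on the result.** With no hypothesis or success criterion, no test is distorted, and section 9 openly admits a limitation. That limits the seriousness. It does not remove the point, because the descriptive mean change is then the main result, and its interpretation depends on how it was measured.

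**Conclusion.** The point holds in a limited form. Sections 9 and 11.6 contradict each other and must be reconciled. No visible text keeps a subject's earlier TBUT, gland and staining values from the follow-up examiner, so anchoring, in either direction, can enter an uncontrolled change from baseline.

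The size is unknown. An assumed drift of 0.5 to 2 s is about 4% to 17% of the pilot's 11.7 s. Drift of that order could not account for a change as large as the pilot's, but it would weigh more on a smaller re-treatment effect or one that wanes over 6 months.

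A reader might infer from the 61% in the working that the primary endpoint is seriously and favorably biased. The documents do not support this: both the size and the direction of the drift are assumed, and no confidence interval is planned. Nor would withholding earlier values make the endpoint free of expectation bias. It would remove an unknown part. Knowledge of treatment, regression to the mean after selection on low TBUT, and the absence of a control all remain. This is a low-cost improvement to a descriptive study, not a flaw that invalidates it.

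**What to change.** Replace the section 9 sentence with: *The study is single-arm and open-label; subjects and examiners know that treatment was given. To limit examiner bias, follow-up exams are not done by the treating clinician, and the examiner records and signs TBUT, gland and staining scores before earlier values are opened.*

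Repeat the recording rule in section 11.6, and add that earlier pages are opened at the same visit, once the scores are signed, for the safety comparison. This keeps the check for worsening signs described in section 13.6. If the redacted part of 11.6 already contains such a rule, only section 9 needs to change.

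The replacement keeps the disclosure that the study is unmasked, which matters because the symptom questionnaires (SPEED, OSDI, SANDE) are still answered by subjects who know they were treated.

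The cost is a short delay within the visit before the safety comparison, and separate visit pages if the forms are not already laid out that way. No extra staff are needed.
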